### 1 STUDY SUMMARY

	<del>-</del>
Study name	Open prospective study to evaluate the safety, tolerability, pharmacokinetics and the effect of food of medicinal product PBTZ169 in 80 mg capsules when used in increasing doses in
	healthy volunteers
Identification	PBTZ169-Z00-C01-3
number/study code	
Study phase	Phase I
Planned study dates	Expected duration of the study – 7 months.
	Recruitment period is approximately 10 days. Maximum duration
	of participation of one volunteer in the study at the first stage (dose
	escalation when used once or twice, effect of food when used once)
	- 24 days, at the second stage (repeated use) – 30 days.
Study goals	At the first stage – study the safety, tolerability and evaluate the
Study gours	pharmacokinetics of PBTZ169, 80 mg capsules, in healthy
	volunteers when administered once or twice on an empty stomach
	successively in increasing doses (640, 960, 1280 mg once a day and
	640 mg twice daily), evaluate the effect of food with single
	administration of the product at a dose of 640 mg.
	At the second stage – study the safety, tolerability and evaluate the
	pharmacokinetics of PBTZ169, 80 mg capsules, in healthy
	volunteers with repeated use for 14 days, at a dose and following a
	regimen (on an empty stomach or after meal, once a day or twice
	day) determined by results of analysis of tolerability, safety and
	pharmacokinetics after the completion of the first stage of the study.
Study objective	
Study Objective	Main objectives
	• Evaluate the safety and tolerability of PBTZ169, 80 mg
	capsules, in healthy volunteers once or twice on an empty
	stomach in increasing doses (640, 960, 1280 mg once daily
	and 640 mg twice daily) and repeated administration for 14
	days at maximum dose and following a regimen determined
	by results of analysis of tolerability, safety and
	pharmacokinetics after the completion of the first stage of
	the study.
	• Evaluate the effect of food on the pharmacokinetics of
	PBTZ169, 80 mg oral capsules at a dose of 640 mg.
	Compare the test (T) method of administration (8 80 mg
	capsules after meal) with the reference (R) method of
	administration (8 80 mg capsules on an empty stomach).
	Secondary objectives
	• Evaluate the safety of PBTZ169 based on all possible
	adverse events.

- Evaluate the effect of PBTZ169 on vital signs (blood pressure, HR, body temperature, RR) and results of physical examination.

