### First stage – dose escalation when used once or twice, effect of food with single administration

Volunteers who meet the selection criteria for the study will be included in 5 cohorts:

✓ Cohort 1A (C1A) – includes 10 healthy volunteers of the main group, each of whom will receive PBTZ169 only twice: during period 1 of the *First stage* of the study on an empty stomach at a dose of 640 mg (8 80 mg capsules once a day) and during period 2 of the *First stage* of the study after meal at a dose of 640 mg (8 80 mg capsules, once a day) and 1 healthy backup volunteer.

- ✓ Cohort 1A (C1A) includes 10 healthy volunteers of the main group, each of whom will receive PBTZ169 only twice: during period 1 of the *First stage* of the study after meal at a dose of 640 mg (8 80 mg capsules once a day) and during period 2 of the *First stage* of the study on an empty stomach at a dose of 640 mg (8 80 mg capsules, once a day) and 1 healthy backup volunteer.
- ✓ Cohort 2 (C2) includes 10 healthy volunteers of the main group, each of whom will receive a single dose of PBTZ169 on an empty stomach at a dose of 960 mg (12 80 mg capsules, once a day) and 1 healthy backup volunteer.
- ✓ Cohort 3 (C3) includes 10 healthy volunteers of the main group, each of whom will receive PBTZ169 twice on an empty stomach at a dose of 640 mg (8 80 mg capsules, twice daily with a 12-hour interval; total daily dose 1280 mg) and 1 healthy backup volunteer.
- ✓ Cohort 4 (C4) includes 10 healthy volunteers of the main group, each of whom will receive a single dose of PBTZ169 on an empty stomach at a dose of 1280 mg (16 80 mg capsules, once a day) and 1 healthy backup volunteer.

Randomization will be done after hospitalization on the day before the first administration of the investigational product (Day 0 of the study) within each cohort by the envelope randomization method. Volunteers of each cohort (C1A, C1B, C2, C3 and C4) will be randomized at a ratio of 10:1:

- main therapy group 10 volunteers who will receive a single dose or two doses of the investigational product;
- group of backup volunteers 1 volunteer who receive one dose or two doses of the investigational product only if one of the volunteers of the main group of this cohort leaves the study before dosing and within 4 hours from the moment of dosing due to a reason unrelated to AE/SAE.

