On an empty stomach the product is administered (by volunteers of cohorts C2 and C4, cohort C1A during period 1, cohort C1B during period 2) after 10 hours of night fasting, washing down 300 mL of bottled water. Each volunteer will administer 4 capsules within 2 minutes broken down into few portions, depending on the total number of capsules, washing down each portion with a few sips of water On the day of administration it is allowed to drink as much water as one wants except for 1 hour prior to administration of the product, during which water consumption is not allowed, and 4 hours after the administration of the product (during the first hour water consumption is not allowed, during the next 3 hours water consumption will be regulated: the volunteer will need to drink 100 mL of bottled water every hour). Within 4 hours after administration, volunteers will not be allowed to eat. 4 hours after administration, volunteers will receive a standard meal.

After food intake (by volunteers of the C1A cohort – during period 2, of the C1B cohort – during period 1) the medicinal product is administered 30 minutes (± 2 minutes) after the beginning of a standard breakfast, washing down with 300 mL of bottled water (within 2 minutes, 4 capsules broken down into few portions depending on the total number of capsules, washing down each portion with a few sips of water). Breakfast is provided after 10 hours of night fasting. On the day of administration it is allowed to drink as much water as one wants except for 30 minutes prior to administration of the product, during which water consumption is not allowed (except for that present in the breakfast), and 4 hours after the administration of the product (during the first hour water consumption is not allowed, during the next 3 hours water consumption will be regulated: the volunteer will need to drink 100 mL of bottled water every hour). Within 4 hours after administration, volunteers will not be allowed to eat. 4 hours after administration, volunteers will receive a standard meal.

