Volunteers of the C3 cohort (two administrations) will take the product twice a day, washing down with 300 mL of bottled water each time (within 2 minutes, 4 capsules broken down into few portions depending on the total number of capsules, washing down each portion with a few sips of water). For the first time, volunteers of the C3 cohort will take the medicinal product in the morning on an empty stomach after 10 hours of night fasting, second time – 12 hours after the first administration after 3 hours of fasting. On the day of administration it is allowed to drink as much water as one wants except for 1 hour prior to each administration of the product, during which water consumption is not allowed, and 4 hours after each administration of the product (during the first hour water consumption is not allowed, during the next 3 hours water consumption will be regulated: the volunteer will need to drink 100 mL of bottled water every hour). Within 4 hours after each administration, volunteers will not be allowed to eat. 4 hours after the first administration, volunteers will receive a standard meal. Standard dinner will be offered to volunteers of the C3 cohort no later than 3 hours before the second administration of the medicinal product.

Each volunteer in the C1A, C1B, C2 and C4 cohorts will have their venous blood collected to determine the concentration of PBTZ169 and its metabolites before the administration of the product (point 0, blood sample in the range from -5 min to -1 min), and then at the following time points after the administration of the medicinal product: at 0:30, 1:00, 1:30, 2:00, 3:00, 4:00, 6:00, 9:00, 12:00, 24:00, 48:00 and 72:00 (h:min).

For volunteers of the C3 cohort (two administrations), venous blood will be collected to determine the concentration of PBTZ169 and its metabolites before the first administration of the medicinal product (point 0, blood sample in the range from -5 min to -1 min), and then within 72 hours at the following times points after each administration of the medicinal product: at 0:30, 1:00, 1:30, 2:00, 3:00, 4:00, 6:00, 9:00, 12:00 (the point before the second administration of the medicinal product in the range from -5 min to -1 min), 12:30, 13:00, 13:30, 14:00, 15:00, 16:00, 18:00, 21:00, 24:00, 48:00, 72:00 (h:min) after the first administration of the medicinal product.

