After the study is completed by the last volunteer from the *First stage* (C1A, C1B, C2, C3 and C4), safety and pharmacokinetics, as well as the effect of food will be analyzed based on the data of all cohorts who administered the product once or twice.

Based on the results of the evaluation of safety, pharmacokinetics and analysis of the effect of food after the end of the *First stage*, the Sponsor:

- ✓ will determine the dose for the study of PBTZ169 with repeated use in Phase 2 of the study.
- ✓ will decide on the mode of administration of PBTZ169: on an empty stomach or after meal, once a day or twice a day.
- ✓ can decide to adjust time points for sampling (if necessary, appropriate amendments will be made to the protocol);
- ✓ can decide to make changes to study procedures at Stage 2 (where necessary, appropriate amendments will be made to the protocol).

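### Cohort C3 is described as two empty-stomach doses, but its second dose follows a stated 3-hour fast and cannot meet the 10-hour condition, so C3 versus C4 is not a purely fasted comparison of dosing frequency

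*Combined protocol and SAP*

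**What the plan says.** In the combined protocol and SAP, the study goals (Study Summary) cover "volunteers when administered once or twice on an empty stomach" in increasing doses, and 640 mg twice daily is on that list. The main safety objective and the secondary pharmacokinetic objective use the same description. The cohort list under *First stage* says of C3, "each of whom will receive PBTZ169 twice on an empty stomach at a dose of 640 mg", and adds "twice daily with a 12-hour interval; total daily dose 1280 mg".

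The administration paragraphs of the same section then set out how the doses are taken:

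- The empty-stomach paragraph opens "On an empty stomach the product is administered (by volunteers of cohorts C2 and C4, cohort C1A during period 1, cohort C1B during period 2". C3 is not in that list. The condition is dosing "after 10 hours of night fasting, washing down 300 mL of bottled water".
- The after-food paragraph doses 30 minutes after the start of a standard breakfast.
- The C3 paragraph applies the empty-stomach description and the 10 h night fast to the first dose only. The second is taken "second time – 12 hours after the first administration after 3 hours of fasting". A standard meal comes 4 h after the first dose, and "Standard dinner will be offered to volunteers of the C3 cohort no later than 3 hours before the second administration of the medicinal product".

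After the First stage the sponsor "will decide on the mode of administration of PBTZ169: on an empty stomach or after meal, once a day or twice a day", using safety, pharmacokinetics and the food-effect analysis.

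**The concern.** The objectives promise the pharmacokinetics of 640 mg twice daily on an empty stomach. Under the C3 procedure, only the first dose is taken in the state that the plan uses for its other empty-stomach cohorts. The second is taken in a third prandial state, which the food-effect crossover in C1A and C1B does not study.

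This is more than loose wording. C3 is the only twice-daily cohort, and C4 is the once-daily cohort with the same daily dose. Anyone choosing the Stage 2 frequency will naturally set C3 beside C4. Those cohorts differ in frequency and in the food state before half the C3 dose. Whether food changes exposure is itself a main objective of the trial, so the plan cannot take the effect of a meal some hours earlier to be nil.

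**Working it through.** **Dose check.** C3 takes 2 × 8 × 80 mg = 1280 mg, which reproduces the plan's stated daily total. C4 takes 16 × 80 mg = 1280 mg. The daily doses are equal, so setting the two cohorts side by side is natural.

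**Timeline for C3** (hours after the first dose, from the C3 administration paragraph):

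- Dose 1 at 0 h, after a 10 h night fast.
- Standard meal at +4 h.
- Dinner offered at 12 − 3 = +9 h at the latest.
- Dose 2 at +12 h, with a stated fast of 3 h.

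The longest fast conceivable before dose 2 ignores dinner altogether and counts from the +4 h meal: 12 − 4 = 8 h. Since 8 h is less than 10 h, no permitted dinner time lets dose 2 meet the condition set for C2, C4 and the fasted periods of C1A and C1B.

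**Prandial states side by side.**

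| Administration | State before dosing |
|---|---|
| C2, C4, C1A period 1, C1B period 2 (food-effect reference) | 10 h night fast |
| C3 dose 1 | 10 h night fast |
| C1A period 2, C1B period 1 (food-effect test) | 30 min after the start of breakfast |
| C3 dose 2 | stated 3 h fast after dinner; cannot exceed 8 h |

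Dose 2 is 640 of 1280 mg, or 50% of the C3 dose.

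**Possible size.** Let A be the AUC of 640 mg after a 10 h fast, and F the AUC ratio of the dose-2 state to that fast. Assume dose-proportional exposure and no effect of frequency. Then the C3 total is A + FA, the C4 total is 2A, and

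C3/C4 = (A + FA) / 2A = (1 + F)/2.

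The share of C3 exposure that comes from dose 2 is F/(1 + F).

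| Assumed F | C3/C4 total AUC | Share from dose 2 |
|---|---|---|
| 0.5 | 0.75 | 33% |
| 0.8 | 0.90 | 44% |
| 1.0 | 1.00 | 50% |
| 1.25 | 1.125 | 56% |
| 2.0 | 1.50 | 67% |

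The documents give no value for F. The C1A/C1B crossover estimates the ratio for dosing 30 min after the start of breakfast, which is a different state, so Stage 1 does not estimate F either. The values in the table are assumptions and include the case of no effect (F = 1).

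**What remains usable.** C3 is sampled at 0:30, 1:00, 1:30, 2:00, 3:00, 4:00, 6:00, 9:00 and 12:00 after dose 1. These are the times used over the first 12 h in C1A and C1B. The C3 profile from 0 to 12 h is therefore a 640 mg profile after a 10 h fast, and it can be compared with the fasted periods of C1A and C1B over the same interval.

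**The case against.** The best defence is that the plan hides nothing. The 10 h condition is written for named cohorts, C3 has its own openly stated procedure, and a site would know what to do. That is correct: the conflict lies between the description in the goals, objectives and cohort list and the C3 procedure. It does not make the procedure unclear.

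A second defence is that the study is called non-comparative, no C3 versus C4 test is planned, and tolerability and safety are the primary criterion for the Stage 2 dose. C3 and C4 also differ in dose per administration (640 against 1280 mg), time of day and carry-over from the first dose, so identical fasting would still not isolate frequency. All of this stands and limits the point. It does not remove it, because the sponsor will still choose frequency and food state from Stage 1 data, and food state is one more difference that the plan's description conceals.

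A third defence is that meals may belong to any realistic twice-daily regimen. They may, but the plan does not say so, and its stated objective is empty-stomach dosing.

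Some stronger readings are tempting and are not supported:

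- A reader might infer that half of C3's *exposure* is unfasted. Only half of the *dose* is known to be. The exposure share depends on F.
- A reader might take the dinner sentence to contradict the 3 h fast, since a meal takes time to eat. The sentence sets a latest time, so an earlier dinner satisfies both statements.
- A reader might fix the gap at about 3 h. The text states 3 h of fasting and sets only a latest time for dinner. The timeline bounds the fast at 8 h.

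**Conclusion.** The point holds. The description of C3 as two empty-stomach doses does not agree with its procedure, and the timeline shows that dose 2 cannot meet the 10 h condition. The objective of characterising 640 mg twice daily on an empty stomach is met for dose 1 only. A C3 versus C4 difference mixes frequency with food state, in addition to dose per administration, time of day and carry-over.

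The mismatch rests on the text and simple timing, and is firm. The size of the consequence is not known. Under dose proportionality and no frequency effect, the C3/C4 total AUC ratio would run from 0.75 (F = 0.5) through 1.00 (F = 1) to 1.50 (F = 2). The documents support neither a particular F nor dose proportionality from 640 to 1280 mg. They therefore do not show that the Stage 2 choice will be biased, only that Stage 1 could not separate a food contribution if one were present.

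**What to change.** Reconcile the empty-stomach description of C3 in the study goals, objectives and cohort list with the empty-stomach and C3 administration paragraphs. Which fasting condition should apply is for the sponsor to decide, and this review takes no position on it.

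As long as the C3 procedure stands as written:

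- Use C3 dose 1 (0 to 12 h) as the fasted 640 mg data from this cohort.
- Report dose 2 under its actual prandial state, using recorded dinner times.
- State, where the post-First-stage decisions are listed, that C3 versus C4 is not a purely fasted comparison of once- with twice-daily dosing.

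The cost is changed wording, a record of meal times and a more limited conclusion from C3. No extra volunteers or blood samples are needed.

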#### Second stage - repeated administration

At the second stage, it is planned to recruit 1 cohort consisting of 10 healthy volunteers, to study the medicinal product with repeated use.

Volunteers who meet selection criteria for the study will be enrolled in the next cohort for multiple product administration:

• Cohort 5 (C5) – includes 10 healthy volunteers, each of whom will receive the medicinal product PBTZ169 at a dose of X mg daily on an empty stomach or after meal, once or twice a day at the same time ±15 minutes for 14 days. It is possible to enroll additional 4 backup volunteer. Backup volunteers will be enrolled as per the decision of the Sponsor only if two or more volunteers from the main group of cohort 5 drop out before Day 7 of the study, for any reason other than AE/SAE, in the same number as there are dropped out volunteers, for which an additional screening will be carried out.

Volunteers will be hospitalized in the evening on the day before the administration of the product, but at least 12 hours before planned

<sup>1 The dose of PBTZ169 and the mode of administration of the product (on an empty stomach or after meal, once or twice a day) will be determined by analyzing the data obtained in the first stage.

administration of the product. Mode of administration of the medicinal product and corresponding restrictions on consumption of food and water will be determined based on the results of the evaluation of safety, pharmacokinetics and analysis of the effect of food with administration of the investigational product once or twice after the *First stage* of the clinical study. For volunteers from the C5 cohort, blood for determination of the concentration of PBTZ169 and its metabolites will be collected before and after the administration of the first, 7th and last (14th) dose of the medicinal product at the following time points: 5 minutes before the administration of the medicinal product (only until the first dose), 0 min and within 24 h after the administration of the first, 7th and last (14th) dose of the medicinal product in: 0:15, 0:30, 1:00, 1:30, 2:00, 3:00, 4:00, 6:00, 8:00, 10:00, 12:00, 24:00 (h:min after the administration of a dose of the medicinal product). During days 3-6 and 9-13 of administration of the medicinal product, in order to determine the concentration of PBTZ169, venous blood will be collected daily at 0 min (before the administration of the medicinal product). After the administration of the last (14th) dose of the medicinal product, blood samples will also be collected at 48 h and 72 h points. During the entire time of administration of the medicinal product and before blood collection at 48 h time point after the last administration of the medicinal product, volunteers will be followed-up in a hospital. Then, after all procedures planned under the protocol, volunteers will be discharged, after which they will be followed up on an outpatient basis. Blood sampling at the time point of 72 hours after the last administration of the medicinal product will be done on an outpatient basis. After discharge from the hospital, volunteers from the C5 cohort will have to visit the research site after 2 days to have their blood sampled at the time point of 72 hours, and also 7±1 days after the last administration of the medicinal product (Day 21±1 of the study) to undergo procedure of follow-up visit (FUV, safety evaluation).

For the following time points, deviations from the specified time of 10 minutes in either direction are allowed ( $\pm$  10 min): 24 h after the administration of the first, 7th and last (14th) dose of the investigational product. For time points of 48 and 72 hours after the administration of the last (14th) dose, deviation from the specified time of 20 minutes in either direction ( $\pm$  20 min) is allowed. For all other time points for blood sampling after the administration of the investigational medicinal product, deviations of not more than 2 min in either direction ( $\pm$  2 min) are allowed. In case of early dropout of a volunteer, in the absence of risk for the volunteer, attempts will be made to collect blood samples from them according to schedule for the last (14th) dose of the medicinal product.

At each time point of blood sampling for the purpose of determination of the concentration of PBTZ169, additional venous blood samples will also be collected for storage for determination of additional parameters should it become necessary. A detailed description of the work with clinical blood samples for the purpose of study of pharmacokinetics will be provided in the instructions prepared by the central laboratory.

After the completion of the first part of the study, main samples (blood plasma samples of volunteers) will be sent to the central laboratory to determine the concentration of the investigational product PBTZ169 and its two metabolites (MET-11526124 3-OXO MET-11526115 3-OH). Additional samples (blood plasma samples of volunteers) will be stored in the research site in a freezer at a temperature not exceeding -65 °C until the end of the pharmacokinetic part of the study or until further directions from the Sponsor.

#### Follow-up period

Follow-up of volunteers from cohorts of the *First stage* (C1A, C1B, C2, C3 and C4) will be 5±1 days after the last dose of the medicinal product. After discharge from the hospital, volunteers will need to visit the research site 5±1 days after the administration of the medicinal product (on Day 12±1 of the study for volunteers of cohorts C1A and C1B or on Day 6±1 of the study for cohort C2-C4) to undergo procedures of follow-up visit (FUV; safety evaluation), after which the volunteers will end their participation in the study.

Total duration of the follow-up period for each volunteer of the C5 cohort (cohort of **Second stage**) is 7±1 days after the last dose of the medicinal product. After discharge from the hospital, volunteers from the C5 cohort will need to visit the research site 7±1 days after the last administration of the medicinal product (Day 21±1 of the study) to undergo procedures of follow-up visit (FUV; safety evaluation), after which volunteers will end their participation in the study.

Maximum duration of participation in the study will be 30 days (for healthy volunteers from cohorts C1A and C1B - 24 days, cohorts C2, C3 and C4 - 18 days, cohort C5 - 30 days).

